17.3 Primary endpoint

The primary endpoint is change from baseline in BMI SDS after 56 weeks of treatment³³.

The objective is to show that liraglutide is superior to placebo in obtaining weight loss. Let $\mu_{\text{liraglutide}}$ and μ_{placebo} denote the mean change in BMI SDS for liraglutide and placebo, respectively. The null-hypothesis and the alternative hypothesis are:

H0: $\mu_{\text{liraglutide}} = \mu_{\text{placebo}}$ against the alternative HA: $\mu_{\text{liraglutide}} \neq \mu_{\text{placebo}}$

The null-hypothesis will be rejected on a 5% level if the two-sided 95% CI of the treatment difference $\mu_{\text{liraglutide}} - \mu_{\text{placebo}}$ excludes 0. If the upper limit is below 0, superiority of liraglutide against placebo can be concluded.

The hypothesis will be tested using an analysis of covariance (ANCOVA) model with treatment, sex, region, baseline glycaemic category, stratification factor for Tanner stage and interaction between baseline glycaemic category and stratification factor for Tanner stage as fixed effects, and baseline BMI SDS and baseline age as covariates. The baseline glycaemic category includes two levels: presence and absence of dysglycaemia. The stratification factor for Tanner stage includes two levels: stages 2 and 3 together, and stages 4 and 5 together.

Missing data in the main analysis will be handled by the following multiple imputation (MI) method. A pattern mixture model approach is applied where withdrawn subjects without a follow-up visit are assumed to respond as if treated with placebo for the entire trial. Multiple copies (100 copies) of the full dataset will be generated by imputing missing values based on estimated parameters for the placebo group. This will be done as follows:

- In the first step, 100 copies of the dataset will be generated.
- In the second step, an enriched ANCOVA model with sex, region, baseline glycaemic category, stratification factor for Tanner stage and interaction between baseline glycaemic category and stratification factor for Tanner stage as fixed effects and baseline BMI SDS, baseline waist circumference, baseline age and baseline HbA_{1c} as covariates will be fitted to the change from baseline in BMI SDS at 56 weeks for the completers in the placebo group only.

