17.4.1 Supportive secondary endpoints

17.4.1.1 Efficacy endpoints

BMI SDS at 30 and 82 weeks

The change in BMI SDS from baseline to 30 and 82 weeks and from 56 weeks to 82 weeks will be analysed using the same statistical method as used for the main analysis of the primary endpoint.

BMI

The changes in BMI from baseline at 30 and 56 weeks will be analysed separately with the same type of ANCOVA with MI as used for the main analysis of the primary endpoint, but with the baseline BMI as covariate instead of the baseline BMI SDS. Change from 56 weeks to 82 weeks will be summarised using descriptive statistics.

In addition, the following categorical endpoints related to BMI will be evaluated:

- Percentage of subjects achieving $\geq 5\%$ reduction in baseline BMI at 30, 56 and 82 weeks
- Percentage of subjects achieving $\geq 10\%$ reduction in baseline BMI at 30, 56 and 82 weeks

These endpoints will be analysed separately using a logistic regression model. The response will be a binary outcome (yes/no) indicating for each subject whether the respective minimum reduction in BMI has been achieved. The model will include treatment, sex, region, baseline glycaemic category, stratification factor for Tanner stage and interaction between baseline glycaemic category and stratification factor for Tanner stage as fixed effects, and baseline BMI and baseline age as covariates. The results will be presented as odds ratios together with the associated 95% CIs.

For the analysis of the categorical endpoints, missing BMI values will be imputed using the 100 complete datasets from the MI performed for the corresponding analysis on the continuous change in BMI. The logistic regression will be performed on each of these datasets. Rubin's formula will then be applied on the 100 estimates of the log odds ratio and the associated SDs to produce a pooled estimate and SD. These pooled values will lastly be used to calculate the 95% CI for the odds ratio.

PRO outcome

The PRO questionnaire IWQOL-Kids will be evaluated similarly to the primary endpoint. That is, the change in PRO score from baseline at 30 and 56 weeks will be analysed separately using the same type of ANCOVA with MI as used for the main analysis of the primary endpoint, but with the corresponding baseline PRO score instead of the baseline BMI SDS as covariate.

Glycaemic category

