The change in glycaemic category (normoglycaemia, pre-diabetes, T2DM) from baseline at 30 and 56 weeks and change from 56 weeks to 82 weeks will be summarised using descriptive statistics.

Furthermore, two separate analyses will be performed on the binary variable normoglycaemia (yes/no) at 30 and 56 weeks, using a logistic regression model with the factors treatment, sex, region, baseline glycaemic category, stratification factor for Tanner stage and interaction between baseline glycaemic category and stratification factor for Tanner stage, and baseline age as covariate. Missing data will be handled by an MI method similar to the one used for the main analysis of the primary endpoint, but adapted to the logistic regression model. The results will be presented as odds ratios together with the associated 95% CIs.

Other supportive secondary efficacy endpoints

The following other efficacy variables will be evaluated:

- Body weight
- Waist circumference
- Waist-to-hip circumference ratio
- Cardiovascular biomarker (hsCRP)

- Fasting lipids (TC, LDL-cholesterol, HDL-cholesterol, non-HDL cholesterol, VLDL cholesterol, TG and FFA)
- Systolic and diastolic blood pressure
- Quantitative glucose metabolism parameters (HbA_{1c}, FPG, fasting insulin, fasting C-peptide, HOMA-B^a and HOMA-IR^a)

The changes in these variables from baseline at 30 and 56 weeks will be analysed using the same type of ANCOVA with MI as used for the main analysis of the primary endpoint, but with the baseline value of the corresponding variable instead of the baseline BMI SDS as covariate. Each endpoint will be analysed separately. For hsCRP, fasting lipids, fasting insulin, fasting C-peptide, HOMA-B and HOMA-IR, the response and baseline values will be log transformed prior to the analysis. The change in these variables from 56 weeks to 82 weeks will be summarised using descriptive statistics.

^a The calculation of the HOMA endpoints will be done as follows:

- Beta-cell function (%) = $20 \cdot \text{fasting insulin}[\text{mU/L}] / (\text{FPG}[\text{mmol/L}] - 3.5)$
- Insulin resistance (%) = $\text{fasting insulin} [\text{mU/L}] \cdot \text{FPG} [\text{mmol/L}] / 22.5$.

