The imputation model in step 2 uses placebo subjects from FAS with non-missing BMI SDS at baseline and week 56. The imputation model is a linear regression of BMI SDS at week 56 on the factors and covariates listed in [Table 2-3](#) (except randomised treatment arm) with interaction term included in the model. The order of the factors and covariates has been retained as mentioned in [Table 2-3](#) while fitting imputation model. The estimated posterior distribution for the parameters (regression coefficients and variances) in the imputation model is then used to impute missing week 56 BMI SDS values for both randomised treatment arms.

Table 2-3: Factors and Covariate for imputation model

Factors and covariates at baseline	Type	Categories	Order
Sex	Factors	Female, Male	1
Region	Factors	Europe, North America	2
Baseline Glycaemic category	Factors	Yes, No	3
Tanner stage	Factors	Stage 2 and 3 together, Stage 4 and 5 together	4
Tanner stage, Glycaemic category	Interaction factor	Not applicable	5
Baseline BMI SDS	Covariate	Not applicable	6
Baseline Waist circumference	Covariate	Not applicable	7
Baseline Age	Covariate	Not applicable	8
Baseline HbA1c	Covariate	Not applicable	9

The multiple imputations will be generated using Novo Nordisk trial number 80224180 as seed number.

A similar procedure of imputation will be followed for all the secondary endpoints as mentioned in [Table 2-4](#) except while imputing missing values for waist circumference assessment, baseline waist circumference which will not be included in the imputation model. Similarly, for HbA_{1c} assessments, baseline HbA_{1c} will not be included in the imputation model.

For missing glycaemic category, the imputation will be done for missing FPG and HbA_{1c} assessments using the imputation model mentioned in [Table 2-4](#) except for HbA_{1c}, baseline HbA_{1c} which will not be used while imputing the missing values.

Table 2-4: Statistical analysis to address primary and secondary objectives

SI No.	Endpoints	Landmark visits	Endpoint type	Imputation approach and Statistical model	Analysis set	Sensitivity analyses
Primary Endpoint						
1	Change from baseline in BMI SDS	Week 56	Continuous	J2R-MI ANCOVA	FAS	
 • ANCOVA (LOCF) • ANCOVA (BOCF) • ANCOVA (no imputation, with 56 week completers) • MMRM
Secondary Endpoint						
2	Change from baseline in BMI SDS	Week 30, Week 82	Continuous	J2R-MI ANCOVA	FAS	NA

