24	Change from baseline in FFA (mmol/L)	Week 30, Week 56	Continuous	J2R-MI ANCOVA (with log transformed response and baseline values)	FAS	NA
25	Change from baseline in HbA1c (%)	Week 30, Week 56	Continuous	J2R-MI ANCOVA	FAS	NA
26	Change from baseline in FPG (mmol/L)	Week 30, Week 56	Continuous	J2R-MI ANCOVA	FAS	NA
27	Change from baseline in fasting insulin (pmol/L)	Week 30, Week 56	Continuous	J2R-MI ANCOVA (with log transformed response and baseline values)	FAS	NA
28	Change from baseline in fasting C-peptide (nmol/L)	Week 30, Week 56	Continuous	J2R-MI ANCOVA (with log transformed response and baseline values)	FAS	NA
29	Change from baseline in HOMA-B	Week 30, Week 56	Continuous	J2R-MI ANCOVA (with log transformed response and baseline values)	FAS	NA
30	Change from baseline in HOMA-IR	Week 30, Week 56	Continuous	J2R-MI ANCOVA (with log transformed response and baseline values)	FAS	NA

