2.4 Secondary endpoints

All the secondary supportive efficacy endpoints listed below will be analysed as per protocol section 17.4.

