3.2 Supportive secondary efficacy endpoints

- All the secondary supportive analysis will be performed on in-trial period.
- To analyse the change in BMI SDS from week 56 to week 82 subjects who have completed the treatment (treatment completers), only their assessment at week 56 will be considered as baseline. No change from week 56 to 82 will be calculated for treatment discontinued subjects and for withdrawn subjects unless they have week 56 visit assessment collected.
- Multiple imputation will not to be considered for change in BMI SDS from week 56 to 82 parameter if there is no missing assessment.
- Tanner stage and glycaemic category collected at randomisation visit will be considered as fixed effect while performing ANCOVA for change from baseline to week 30, 56 and 82 and change from week 56 to 82.
- For “percentage of subjects achieving $\geq 5\%$ reduction” and “Percentage of subjects achieving $\geq 10\%$ reduction” in baseline BMI at week 30, 56 and 82. Missing imputation will be handled as mentioned in section [2.3](#) with the baseline BMI as covariate instead of baseline BMI SDS.
- Body weight with standard units (Kg) will only be used in all summary and analysis outputs.

Below additional supportive secondary endpoint is been included in section [2.4](#)

- Change from baseline to 30 and 56 weeks in:
 - BMI SDS (%)

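### SAP 2.3.2, read literally, takes baseline waist and baseline HbA1c out of the imputation models for their own endpoints and never states the own-baseline swap that would put them back

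*SAP*

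**What the plan says.** **SAP 2.3.2 and Table 2-3.** The imputation model is fitted in placebo subjects. Its covariates are sex, region, glycaemic category, Tanner group and their interaction, then baseline BMI SDS, waist, age and HbA1c. The section extends this to every secondary endpoint in Table 2-4, "except while imputing missing values for waist circumference assessment, baseline waist circumference which will not be included in the imputation model". A matching sentence covers HbA1c. For glycaemic category, FPG and HbA1c are imputed separately, and baseline HbA1c is again something "which will not be used while imputing the missing values" of HbA1c. No substitute covariate is named.

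**Protocol 17.3.** The imputation model for BMI SDS has the same factors "as fixed effects and baseline BMI SDS, baseline waist circumference, baseline age and baseline" HbA1c.

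**Protocol 17.4.1.1.** The other continuous efficacy endpoints, including waist and HbA1c, use the same type of ANCOVA with MI, but "with the baseline value of the corresponding variable instead of the baseline BMI SDS as covariate". The BMI paragraph has the parallel wording, "but with the baseline BMI as covariate instead of the baseline BMI SDS". IWQOL-Kids is treated likewise.

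**SAP 2.4** says the supportive efficacy endpoints "will be analysed as per protocol section 17.4".

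**SAP 3.2** writes a swap into the imputation step once, for the BMI responder endpoints: "with the baseline BMI as covariate instead of baseline BMI SDS". SAP section 3, which lists changes from the protocol, does not mention the waist and HbA1c exclusions.

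**The concern.** A subject's own starting value is usually among the best predictors of a missing later value, and the analysis ANCOVA adjusts for it. An imputation model that omits a covariate used in the analysis model produces noisier imputations than the data allow. It can also shift the treatment difference when dropout is related to that covariate differently in the two arms.

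Two programmers could build different models from this text. One takes 2.3.2 at its word and fits waist on baseline BMI SDS, age, HbA1c and the factors. The other reads protocol 17.4.1.1 into it and fits waist on baseline waist, age, HbA1c and the factors. At stake are the precision and reproducibility of supportive secondary results. HbA1c is among the endpoints the protocol marks for public disclosure.

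**Working it through.** **1. The texts side by side.** Baseline continuous covariates in the imputation model under each reading:

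| Reading | Waist endpoint | HbA1c endpoint | Endpoint not in Table 2-3 (e.g. weight, FPG) |
|---|---|---|---|
| Protocol, swap in analysis step only | BMI SDS, **waist**, age, HbA1c | BMI SDS, waist, age, **HbA1c** | BMI SDS, waist, age, HbA1c; own baseline absent |
| Protocol, swap in imputation step too | **waist**, age, HbA1c | waist, age, **HbA1c** | **own**, waist, age, HbA1c |
| SAP 2.3.2, literal | BMI SDS, age, HbA1c; own baseline absent | BMI SDS, waist, age; own baseline absent | BMI SDS, waist, age, HbA1c; own baseline absent |
| SAP 2.3.2 with unstated swap | **waist**, age, HbA1c | waist, age, **HbA1c** | **own**, waist, age, HbA1c |

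For waist and HbA1c, the protocol keeps own baseline whichever way its swap is read; only the literal SAP removes it. For the other endpoints, everything depends on whether the swap reaches the imputation step, and neither document says so outright.

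**2. The plan's own figure.** Protocol 17.1 gives 228 from a difference of 0.26, SD 0.35, 40% withdrawal and 90% power.
- Diluted difference: 0.26 × (1 − 0.40) = 0.156.
- Variances: placebo 0.35² = 0.1225; active 0.1225 + 0.26² × 0.4 × 0.6 = 0.1387; averaged SD 0.361.
- The noncentral-t calculation gives 114 per arm, 228 in total, with power 90.3%.

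This rests on BMI SDS, whose own baseline stays in Table 2-3, so nothing here changes it.

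**3. Why the response scale matters.** Take own baseline X and the week-56 value Y in SD units, with correlation ρ between them, and let the retained covariates correlate r with X. Residual variance of the imputation model:
- own baseline in: 1 − ρ²
- own baseline out, level imputed: 1 − ρ²r²
- own baseline out, change imputed: 1 − ρ² + (1 − ρ)²(1 − r²)

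With ρ = 0.8 and r = 0.7 these are 0.360, 0.686 and 0.380, so the residual SD ratios are √(0.686/0.360) = 1.38 for level and √(0.380/0.360) = 1.03 for change. With ρ = 0.9 and r = 0.7 they are 0.190, 0.603 and 0.195, with ratios 1.78 and 1.01. SAP 2.3.2 regresses the week-56 level; protocol 17.3 fits change.

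**4. Effect on the treatment comparison.** This was simulated with 114 per arm, placebo-based imputation, ANCOVA on change adjusted for own baseline, and Rubin pooling. Only the 40% comes from the documents (assumed withdrawal; retrieved week-56 visits would lower the missing share). The other inputs are assumptions: for waist, ρ = 0.8–0.9 and r = 0.7–0.9; for HbA1c, ρ = 0.5–0.7 with dysglycaemia status retained. Ratios compare own baseline omitted with included:

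| | Waist | HbA1c |
|---|---|---|
| Pooled SE, level, 40% missing | 1.13–1.66 | 1.08–1.22 |
| Pooled SE, level, 20% missing | 1.08–1.45 | 1.05–1.15 |
| Spread of estimates, level, 40% missing | 1.09–1.49 | 1.03–1.14 |
| Pooled SE, change, 40% missing | 1.00–1.02 | 1.04–1.08 |

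**5. Bias of a null difference**, level imputed, 40% missing, log-odds of dropout 0.5 per baseline SD where related:
- dropout unrelated to own baseline, or related equally in both arms: about 0.01 SD at most
- related in one arm only: 0.02–0.06 SD (waist), 0.04–0.06 SD (HbA1c)
- opposite directions in the two arms, a deliberately adverse case: 0.04–0.10 SD and 0.08–0.11 SD
- own baseline in the model: about 0.01 SD at most throughout

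**The case against.** The strongest reply is that the exceptions make sense only if the swap is already assumed. Waist and HbA1c are the endpoints other than BMI SDS whose baseline is already in Table 2-3. They are therefore the ones that would carry own baseline twice after it replaces baseline BMI SDS. Without a swap the exceptions have no evident purpose. SAP 2.4 imports protocol 17.4, and SAP 3.2 shows the authors applying the swap inside imputation for the BMI responders. On that reading nothing departs from the protocol, so the silence of SAP section 3 proves little.

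This argument is good as to intent, and it largely stands. It does not cure the text. Section 2.3.2 says that the covariate is not included, not that it is entered only once, and protocol 17.4.1.1 does not say that its swap covers the imputation step.

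It is also fair to say that the size depends on assumed correlations. A simpler simulation with one retained covariate (ρ = 0.7–0.9, r = 0.5–0.8) gave ratios of 1.13–1.86 and a bias of 0.06–0.16 SD in the opposite-direction case. The figures show an order of magnitude, not a forecast.

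**Conclusion.** The point holds as a wording defect of minor severity. As written, SAP 2.3.2 drops own baseline for waist, HbA1c and the HbA1c part of glycaemic category. The missing swap leaves the other secondary endpoints in doubt as well. Followed literally with the level imputed, the main cost is wider intervals: a pooled SE ratio of about 1.1–1.7 for waist and 1.1–1.2 for HbA1c at 40% missing, under the stated assumptions. With change imputed, width is almost unchanged.

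A reader might infer more than the documents support:
- **That the endpoints will be imputed without own baseline.** The text permits this, but the likelier intent is the opposite.
- **That the treatment differences are biased.** Bias needs dropout that depends on own baseline differently by arm, and the documents give no evidence of that.
- **That the normoglycaemia result would shift by as much as HbA1c alone might suggest.** The analysed category combines FPG and HbA1c, so misclassification on one analyte overstates the effect.
- **That the primary conclusion or N=228 is at risk.** Neither is touched.

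**What to change.** Replace the exception sentences in SAP 2.3.2 with:

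> For each secondary endpoint and landmark week, the Table 2-3 model is used with the endpoint's own baseline in place of baseline BMI SDS, on the same scale as the response (log where the endpoint is log transformed); where that baseline is already in Table 2-3 (waist, HbA1c) it is entered once. For glycaemic category, FPG is imputed with baseline FPG and HbA1c with baseline HbA1c in the model.

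The week 56-to-82 change stays under SAP 3.2. With own baseline in the model on the response scale, imputing the level or the absolute (or log) change gives equivalent results, which also settles the difference between SAP 2.3.2 and protocol 17.3 for those responses. The glycaemic category sentence should also cite Table 2-3, where the covariates are listed; it now cites only Table 2-4. If the omission is in fact intended, SAP section 3 should list it as a change, with a reason.

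The cost is two or three sentences in the SAP. No protocol amendment or new data are needed, because the baseline values are already collected. Imputation programs already written to the literal text would need adapting.

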3	Change from baseline in BMI SDS (%)	Week 30, Week 56	Continuous	J2R-MI ANCOVA	FAS	NA
4	Change from baseline in BMI SDS	Week 56 to 82 (Week 56 as baseline)	Continuous	J2R-MI ANCOVA	FAS	NA
5	Change from baseline BMI	Week 30, Week 56	Continuous	J2R-MI ANCOVA	FAS	NA

	(Kg/m ²)					
6	Percentage of Subjects achieving $\geq 5\%$ reduction in baseline BMI	Week 30, Week 56, Week 82	Categorical	J2R-MI Logistic Regression	FAS	NA
7	Percentage of Subjects achieving $\geq 10\%$ reduction in baseline BMI	Week 30, Week 56, Week 82	Categorical	J2R-MI Logistic Regression	FAS	NA
8	Change from Baseline in PRO score (IWQoL)	Week 30, Week 56	Continuous	J2R-MI ANCOVA	FAS	NA
9	Change from baseline in Glycaemic category	Week 30, Week 56	Categorical	J2R-MI Logistic Regression	FAS	NA
10	Change from baseline in Body weight (kg and %)	Week 30, Week 56	Continuous	J2R-MI ANCOVA	FAS	NA
11	Change from baseline in Waist circumference (cm)	Week 30, Week 56	Continuous	J2R-MI ANCOVA	FAS	NA
12	Change from baseline in Waist-to-hip circumference ratio (ratio)	Week 30, Week 56	Continuous	J2R-MI ANCOVA	FAS	NA
13	Change from baseline Systolic Blood Pressure (mmHg)	Week 30, Week 56	Continuous	J2R-MI ANCOVA	FAS	NA
14	Change from	Week 30,	Continuous	J2R-MI	FAS	NA

	baseline Diastolic Blood Pressure (mmHg)	Week 56		ANCOVA		
15	Change from baseline Pulse (beats/min)	Week 30, Week 56	Continuous	J2R-MI ANCOVA	SAS	NA
16	Change from baseline in Cardiovascular biomarker (hsCRP) (mg/L)	Week 30, Week 56	Continuous	J2R-MI ANCOVA (with log transformed response and baseline values)	FAS	NA
17	Change from baseline in TC (mmol/L)	Week 30, Week 56	Continuous	J2R-MI ANCOVA (with log transformed response and baseline values)	FAS	NA
18	Change from baseline in LDL-cholesterol (mmol/L)	Week 30, Week 56	Continuous	J2R-MI ANCOVA (with log transformed response and baseline values)	FAS	NA
19	Change from baseline in HDL-cholesterol (mmol/L)	Week 30, Week 56	Continuous	J2R-MI ANCOVA (with log transformed response and baseline values)	FAS	NA
20	Change from baseline in non-HDL cholesterol (mmol/L)	Week 30, Week 56	Continuous	J2R-MI ANCOVA (with log transformed response and baseline values)	FAS	NA
21	Change from baseline in VLDL (mmol/L)	Week 30, Week 56	Continuous	J2R-MI ANCOVA (with log transformed response and baseline values)	FAS	NA
23	Change from baseline in TG (mmol/L)	Week 30, Week 56	Continuous	J2R-MI ANCOVA (with log transformed response and baseline values)	FAS	NA

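### Pulse is modelled only by jump-to-reference with no on-treatment estimate beside it, and SAP 2.3.2 leaves unclear whether the non-BMI endpoints keep their own baseline in the imputation model

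*SAP*

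**What the plan says.** **Pulse.** Row 15 of SAP Table 2-4, "Change from baseline Pulse (beats/min", is analysed at weeks 30 and 56 by jump-to-reference (J2R) multiple imputation and ANCOVA on the safety analysis set. The sensitivity column reads NA. The method comes from protocol 17.4.1.2, which asks for pulse to be analysed like blood pressure and adds summary statistics and shift tables by arm. SAP 2.7 puts the descriptive summaries on the in-trial period, which protocol 17.4.1.2 runs to the last study visit. Protocol 17.4.1.2 also defines an on-treatment period, but for adverse events and hypoglycaemic episodes.

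**Imputation models.** For BMI SDS, SAP 2.3.2 says: "The imputation model is a linear regression of BMI SDS at week 56" on the Table 2-3 terms, which include baseline BMI SDS, waist, age and HbA1c. It continues: "A similar procedure of imputation will be followed for all the secondary endpoints as mentioned in" Table 2-4. Two exceptions follow. For waist the SAP names "baseline waist circumference which will not be included in the imputation model", and for HbA1c it drops baseline HbA1c in the same way. For glycaemic category, FPG and HbA1c are to be imputed "using the imputation model mentioned in" Table 2-4, although the model is in Table 2-3.

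**Text pointing to substitution.** SAP 2.4 states: "All the secondary supportive efficacy endpoints listed below will be analysed as per protocol section 17.4". Protocol 17.4.1.1 uses the ANCOVA with multiple imputation for the other efficacy variables, "but with the baseline value of the corresponding variable instead of the baseline BMI SDS as covariate". SAP 3.2 imputes the BMI-responder endpoints "with the baseline BMI as covariate instead of baseline BMI SDS".

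**The concern.** **(a)** Protocol 17.3 defends the imputation as conservative for the effect on BMI SDS. Applied to a harm, the same shrinkage toward placebo makes the drug look safer. Protocol 18.1 reports a mean rise in resting pulse and lists cardiovascular disorders as an important potential risk because the long-term meaning of that rise is not established. SAP 2.3.2 imputes placebo-like values for subjects missing on treatment as well as for drop-outs. The report would therefore hold only a diluted pulse difference, with no on-treatment difference to set beside it.

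**(b)** An endpoint's own baseline is usually its best single predictor. A programmer following 2.3.2 to the letter would leave it out for waist and HbA1c, and would have no instruction in that section to add it for pulse, blood pressure, lipids, body weight or FPG. Two programmers could reach different secondary results from the same data.

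**Working it through.** **1. The plan's own dilution.** Inputs from protocol 17.1: completer difference 0.26, SD 0.35, 40% withdrawal with withdrawn subjects responding as placebo, 90% power, two-sided 5%.
- Diluted difference: (1 − 0.4) × 0.26 = 0.156.
- Active-arm variance: 0.35² + 0.4 × 0.6 × 0.26² = 0.1225 + 0.0162 = 0.1387. Placebo variance: 0.1225. Average 0.1306, SD 0.3614.
- A two-sample t calculation gives 228 in total (power 90.1% at 114 per arm). The same method reproduces all 18 cells of Table 17-1.

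The sponsor's own sample size therefore already treats this imputation as multiplying a difference by one minus the imputed share.

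**2. The same factor applied to pulse.** Expected J2R difference = (1 − f) × on-treatment difference, where f is the imputed share of the liraglutide arm. This assumes the same on-drug effect in subjects with missing data. Protocol 18.1 gives 2–3 beats/min and does not say whether that is placebo-adjusted or on-treatment; it is assumed here to be the on-treatment difference.

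| f | J2R difference (beats/min) |
|---|---|
| 10% | 1.8–2.7 |
| 20% | 1.6–2.4 |
| 30% | 1.4–2.1 |
| 40% | 1.2–1.8 |

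40% is an upper case: the planned withdrawal share with no retrieved values. In simulation (114 per arm, assumed SD 10, baseline correlation 0.5), true differences of 2 and 3 gave 1.23 and 1.78 at 40% missing under J2R, against 2.06 and 2.98 with own-arm imputation. The 95% CI half-widths were 2.7 and 3.0. At 20% missing, J2R gave 1.62 and 2.39, with half-width 2.5. The issue is the size of the reported estimate, not power.

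**3. Which endpoints lack their own baseline on a literal reading of 2.3.2.**
- BMI SDS rows: own baseline is in Table 2-3.
- BMI responders: substitution stated in SAP 3.2. Continuous BMI follows, because protocol 17.4.1.1 takes the responder data from that imputation.
- Waist and HbA1c: own baseline expressly removed.
- The other non-BMI endpoints: 2.3.2 is silent. Protocol 17.4.1.1 supplies the substitution for the continuous efficacy endpoints. Pulse gets it only through its likeness to blood pressure. The protocol's normoglycaemia model has no such substitution.

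**4. Cost if own baseline is omitted.** Simulated pooled SEs (Rubin) in SD units: 114 per arm, 40% missing, final ANCOVA adjusted for own baseline, no retained covariate correlated with it. The correlations are assumed.

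| Baseline to week-56 correlation | 0.5 | 0.7 | 0.8 |
|---|---|---|---|
| Own baseline included | 0.140 | 0.117 | 0.098 |
| Omitted, week-56 value imputed | 0.156 | 0.151 | 0.148 |
| Omitted, change imputed | 0.157 | 0.124 | 0.102 |

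The increases are about 11%, 30% and 50% for the value, and 12%, 6% and 4% for the change. Both rows matter because SAP 2.3.2 models the week-56 value while protocol 17.3 models the change. With own baseline in the model the two are equivalent, since only its coefficient shifts by one.

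The pooled SE overstates the real loss. With the value imputed, the sampling SD of the estimate rose by 5%, 15% and 29% in one simulation and by about 3–26% in another; with the change imputed it rose by 0–5%. If a retained covariate correlates 0.8 with own baseline, the pooled SE rises only 4–22% (value) or 1–4% (change).

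**5. Bias.** There is none when drop-out is unrelated to baseline. With assumed liraglutide drop-out log-odds of +0.5 or −0.5 per baseline SD and 40% missing, a target of −0.24 SD was estimated between −0.15 and −0.33 with no correlated covariate, and between −0.21 and −0.27 with one correlated 0.8. With own baseline included, all cells lay between −0.236 and −0.247.

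**The case against.** **On pulse.** J2R is prespecified and a legitimate treatment-policy-type estimate. By-arm summaries and shift tables exist. Clinically significant pulse worsening must be reported as an adverse event (protocol 8.4.3), and adverse events have on-treatment output. An independent committee reviews unblinded safety data. All of this stands, and a reader should not infer that J2R is invalid for pulse or that pulse goes unmonitored. But none of it yields an on-treatment mean difference.

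A reader might also infer that the in-trial pulse values are largely off-drug, because SAP 3.4.1 reallocates V25 and V26 records of discontinued subjects. The documents do not support that. Under Table 3-1 only records on days 194–225 or 376–400 reach weeks 30 and 56 (the windows widen for measures taken less often), and a collected record takes precedence over a reallocated one. The pulse row of the flowchart could not be read in the text available, so neither pulse collection at the extra visits nor the real imputed share can be checked.

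**On own baseline.** Protocol 17.4.1.1, SAP 2.4 and SAP 3.2 all point to substitution. SAP section 3, which lists changes from the protocol, does not remove own baseline. The procedure is described as similar, not identical. The waist and HbA1c exclusions make sense if they only stop a covariate entering twice. This is persuasive about intent, but 2.3.2 does not say it, and for waist and HbA1c it says the opposite on its face.

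**Conclusion.** **(a)** Holds as a cheap improvement. A named potential risk is estimated only by a method that shrinks it by the imputed share: from 2–3 to 1.2–1.8 beats/min at an upper-case 40%, or 1.6–2.4 at 20%, if the protocol's figure is the on-treatment difference.

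**(b)** Holds as an ambiguity to clear up, not a proven omission. It is tempting to conclude that the BMI SDS imputation was carried over unadapted and that every secondary endpoint loses its own baseline. That is not so. The BMI SDS, BMI and BMI-responder rows keep theirs, and the SAP makes specific exceptions and log transformations for other endpoints.

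It would also be wrong to read the 50% figure as lost precision. It is a worst-case widening of reported intervals on a literal reading; the true sampling SD rises by about half that or less. The worst case is unlikely for waist, which keeps baseline BMI SDS, and for HbA1c, which keeps baseline glycaemic category. Bias needs drop-out that depends on baseline. The correlations, pulse SD and drop-out log-odds are assumptions; the documents give none of them.

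Neither part affects the primary analysis or N = 228.

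**What to change.** **(a)** Keep row 15 and replace NA with: *Supplementary on-treatment analysis (SAS): MMRM of the protocol 17.3 form for change in pulse, with baseline pulse replacing baseline BMI SDS, using assessments dated from first dose to the last day on trial product.* Add on-treatment pulse descriptives to SAP 2.7. The window has to be stated because the protocol's on-treatment period is written for event onset and extends up to 14 days past the last dose. At the 13-hour half-life in protocol 5.5 that is 336 / 13, or about 26 half-lives.

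**(b)** In SAP 2.3.2 replace the waist and HbA1c exclusions with: *For each endpoint other than BMI SDS, the endpoint's own baseline replaces baseline BMI SDS in the Table 2-3 model and is entered once; the same FPG and HbA1c imputations are used for rows 9, 25 and 26.* Correct the glycaemic-category reference from Table 2-4 to Table 2-3 (editorial).

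**Cost.** One extra analysis on data already collected and a few lines of SAP text. The on-treatment analysis assumes data missing at random, which may fail if subjects stop because of intolerance, and the reported pulse figure may be less favourable.
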